4.6 Study Outcome Measures and Ascertainment

4.6.1 Primary Outcome

The primary outcome is maternal death or transfusion of packed red blood cells by discharge from the hospital or 7 days postpartum, whichever is sooner

4.6.2 Major Secondary Outcome

1. Estimated blood loss collected from anesthesia record and operative report

4.6.3 Secondary Outcomes

- A composite of treatments and interventions in response to bleeding and related complications, within 7 days postpartum. Included are surgical or radiologic interventions to control bleeding and related complications, uterotonics other than oxytocin, open label TXA or other antifibrinolytics, and transfusion of any blood product. Treatments administered as prophylaxis are not included. [Individual components of the composite are described in more detail below.]
- 2. Maternal death or transfusion of packed red blood cells by 7 days postpartum
- 3. A composite of surgical or radiologic interventions to control bleeding and related complications within 7 days postpartum, or maternal death
- 4. A composite of maternal death, thromboembolic events (venous or arterial), ischemic stroke, myocardial infarction, new-onset seizure activity, or admission to the intensive care unit for more than 24 hours, within 6 weeks postpartum
- 5. Transfusion related acute lung injury (TRALI): defined as a ratio of partial pressure of oxygen to inspired fraction of oxygen below 300 within 6 hours of receiving a blood product with bilateral pulmonary edema on chest x-ray and no other cause
- 6. Transfusion of other blood products including fresh frozen plasma, cryoprecipitate, and platelets or administration of any factor concentrates by 7 days postpartum
- 7. Transfusion of 4 or more units of packed red blood cells by 7 days postpartum

- 8. Acute kidney injury: defined as an acute elevation of serum creatinine of ≥ 0.3 mg/dL during a period of 48 hours within 7 days postpartum
- 9. Thromboembolic events (venous or arterial), ischemic stroke, or myocardial infarction within 6 weeks postpartum since the majority of events occur within 6 weeks postpartum³² (safety)
- 10. New-onset seizure activity within 6 weeks postpartum (safety)
- 11. Postpartum infectious complications within 6 weeks postpartum (e.g., endometritis, surgical site infection, pelvic abscess)
- 12. Admission to the intensive care unit for more than 24 hours
- 13. Maternal death within 6 weeks postpartum
- 14. Use of uterotonics other than oxytocin (e.g., prostaglandins, methergine) and quantity used in first 48 hours post delivery
- 15. Surgical or radiologic interventions to control bleeding and related complications within 7 days postpartum (e.g. laparotomy, evacuation of hematoma, hysterectomy, uterine packing, intrauterine balloon tamponade, interventional radiology)
- 16. Change in hemoglobin from before cesarean to lowest measured in first 48 hours postpartum
- 17. Maternal TXA-related side-effects (nausea, vomiting, dizziness)
- 18. Open label use of TXA or other antifibrinolytic
- 19. Length of stay after delivery
- 20. Re-admission within 6 weeks postpartum
- 21. Any transfusion-associated reactions within 7 days postpartum.

Central blinded chart reviews will be conducted by the protocol subcommittee to confirm the accuracy of the following diagnoses: transfusion related acute lung injury (TRALI), thromboembolic events, ischemic stroke, myocardial infarction, and new-onset seizure activity.

5 Statistical Considerations

5.1 Data Relevant to the Primary Outcome

Using data from the MFMU Network Cesarean Registry, the rate of packed RBC transfusion in the entire cohort of 57,169 women was 2.6%. The rate of packed RBC transfusion was 3.2% (762/23,486) in women undergoing primary cesarean and 2.2% (735/33,683) in those undergoing repeat cesarean.³³ When the analysis was limited to those who underwent cesarean without labor, the overall rate of blood transfusion was 2.4% (the rate of packed RBC transfusion for 1st, 2nd, 3rd and 4th cesarean were 4.05%, 1.53%, 2.26%, and 3.65%).³⁴

In a more recent cohort (APEX study) consisting of a random sample of approximately one third of deliveries over a 3-year period, 29,343 women with a cesarean delivery did not meet trial exclusions, and had at least 2 hours from admission to delivery. The rate of RBC transfusion or death in this group of women was 2.8% (811/29,343). In the subset of the 29,343 women who had an unscheduled cesarean delivery the primary outcome rate was 3.5 % (584/16,859). Among those who had scheduled cesareans, the rate of packed red blood cells (RBC) or maternal death was 1.8% (227/12,484).

Based on these 2 large cohorts, the expected rate of the primary outcome in the women undergoing scheduled cesarean delivery is 1.5-2 % and in the women undergoing unscheduled cesarean delivery is 3.5%.

In the Cochrane review, the 95% range of the effect size of TXA was between 46% and 90% reduction in the need for blood products transfusion (RR 0.23, 95% CI 0.10 to 0.54, five trials, 1,259 participants compared with placebo).²¹ For this study a relatively conservative effect size is used of 33-40%.

5.2 Sample Size and Power

The table below provides the sample size calculations needed to achieve 80-90% power to detect 30-40% difference in the primary outcome between women receiving TXA or placebo at time of their cesarean, using a two-tailed alpha of 0.05. The Poisson approximation to the normal distribution was used in the estimation of the sample sizes.

Table 1. Total Sample Sizes for TXA vs. Placebo for Various Primary Outcome Rates

Risk reduction	Power (%)	Primary Outcome Rate in Placebo Group			
(%)	(70)	1.5%	2.5%	3.5%	
30	80	19,800	11,900	8,500	
	85	22,700	13,600	9,700	
	90	26,500	15,900	11,400	
33.3	80	15,700	9,500	6,800	
	85	18,000	11,000	7,700	
	90	21,100	12,700	9,000	
35	80	14,100	8,500	6,100	
	85	16,200	9,700	7,000	
	90	18,900	11,400	8,100	
40	80	10,500	6,300	4,500	
	85	12,000	7,200	5,200	
	90	14,000	8,500	6,000	

Since quotas will be issued to ensure approximately equal enrollment between scheduled and unscheduled cesareans, a sample size of 11,000 women (5,500 in the scheduled and 5,500 unscheduled) will achieve 85% power to detect a 33% reduction in primary outcome overall, assuming that the placebo rate is 2.5%.

The power to detect an interaction between treatment effect and scheduled versus unscheduled cesarean delivery (see Section 5.5.1) was estimated under the following assumptions: 1.5% outcome rate in the placebo group in the scheduled cesarean deliveries, 3.5% primary outcome rate in the placebo group in the unscheduled cesarean deliveries, no overall reduction in the primary outcome. With a sample size of 11,000, there is more than 85% power to detect an odds ratio for 3 for the interaction in a logistic regression and more than 75% if the odds ratio is 2.5.35

If there is a significant interaction between treatment effect and scheduled versus unscheduled cesarean delivery (Section 5.5.1) the effect of treatment within each group will be presented separately. There is more than 85% power to detect a 40% reduction in the primary outcome within the unscheduled cesarean deliveries and more than 75% power to detect a 50% reduction within the scheduled cesarean group.

For the major secondary outcome of estimated blood loss, the sample size calculation is based upon the Wilcoxon Rank Sum test, which depends on the specification of P(X>Y) where X is an observation from the TXA group and Y an observation from the placebo group. Under the null hypothesis this quantity is 0.5. In the APEX study mean blood loss was 800 with a standard deviation of close to 250. The distribution is approximately symmetric. Under the assumption of normality, but assuming a larger standard deviation of 300 to be conservative, there is ample power to detect P(X>0) of 0.477 or greater which corresponds to a median difference between the two groups of 25cc.

5.3 Feasibility

The feasibility of answering the primary research question will be addressed after the first 2000 patients (approximately 1000 placebo patients) have been randomized and the postpartum period completed. This is sufficient for a confidence interval half-width of no more than 1%, if the number of primary outcome cases observed is 25 or less. The primary outcome rate in the placebo group will be presented to the Data and Safety Monitoring Committee (DSMC) without any comparison by group. The DSMC will be charged with making a recommendation regarding potential revision of the sample size in addition to addressing the feasibility of answering the primary research question.

5.4 Interim Analysis

The DSMC meets in person at least once per year and more often if recommended by the committee. For this trial, the DSMC will conduct a six-monthly regular safety review of cumulative adverse events.

Before each of the annual meetings, a formal detailed report will be written by the Biostatistical Coordinating Center (BCC) which presents all baseline variables, protocol adherence, side effects, all adverse events reported, as well as center performance in terms of recruitment, data quality, loss to follow-up and protocol violations.

Once a sufficient number of patients have been accrued into the trial, the report will also include a formal interim analysis evaluating the primary outcome by treatment group. For this evaluation, a cohort of patients is chosen consisting of all patients randomized before a certain date so that the analysis cohort is unaffected by delayed outcome reports.

The main statistical issue relevant to interim analysis is the problem of performing multiple tests of significance on accumulating data. For this trial, the group sequential method of Lan and DeMets will be used to characterize the rate at which the type I error is spent.³⁶ This method is flexible with regard to the timing of the interim analyses.

Asymmetric stopping boundaries will be used for the Lan-DeMets procedure. The upper boundary which describes the stopping rule for benefit will be based on 1-sided type I error of 0.025 and the Lan-DeMets generalization of the O'Brien-Fleming boundary. The lower boundary will be based on a less stringent stopping rule: 1-sided type I error of 0.05 and the Lan-DeMets generalization of the Pocock-type boundary. If the primary outcome is significant or the trial is stopped early for benefit, the methods of Maurer and Bretz will be used to test formally the major secondary endpoint of estimated blood loss while controlling the familywise error rate.³⁷

In addition, the BCC will continuously monitor potential cases of serious adverse events in the active arm during the trial (defined as maternal death or thromboembolism). If the number of such events that occur in the postpartum period meets the number in the table below, recruitment for the study will immediately halt until the DSMC has met and reviewed all of the data to determine whether the trial should continue. The numbers were calculated assuming a 0.1% background rate of one of these events occurring post-cesarean delivery in the general population. Assuming the observed event rate is larger than the background rate, for each N (number of patients recruited), the smallest number of events was calculated such that the probability of the observed event rate occurring given the background rate is less than 5 percent.

Number of Patients in TXA Group	Number of Events
Up to 383	2
384 to 905	3
906 to 1537	4
1538 to 2239	5
2240 to 2992	6
2993 to 3782	7
3783 to 4601	8
4602 to 5443	9
5443 upwards	10

It is often useful to calculate conditional power given the observed data to date, and conditional on the future data showing the originally assumed design effect. If this conditional power is low (under 10 percent) the DSMC may consider termination for futility if the accrual rate is slow with confidence that the Type II error is not greatly inflated.³⁸

It is recognized that any decision to terminate the study would not be reached solely on statistical grounds but on a number of complex clinical and statistical considerations.

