Appendix A Design Summary

OBJECTIVE: To determine whether intraoperative tranexamic acid reduces the need for red blood cell transfusion in women undergoing cesarean delivery.

ORGANIZATION		SCHEDULED EVALUATIONS	/ DATA COLLECTION
Clinical Centers:	Magee, UAB, Ohio State, Utah, Brown, Columbia, Case Western, UT-Houston, UNC, Northwestern, UTMB-Galveston, U Penn	Pre-randomization:	 Hemoglobin and hematocrit Pregnancy, exposure and medical history Gestational age
Subcommittee: DESIGN	[name] (Chair)	Post-randomization:	 Delivery and post-operative data Hemoglobin and hematocrit 0-48 hours post-delivery Phone call to assess readmissions and treatments at 1-2 weeks postpartum Phone call to assess complications and treatments at 6 weeks postpartum
Major Eligibility Criteria:	Cesarean deliverySingleton or twin gestation	MANAGEMENT PROTOCOL	
Groups:	Tranexamic acid (TXA)Placebo	Both Groups:	 Study medication infused immediately after cord clamping, and run over 10 minutes
Random Allocation:	 Simple randomization; 1:1 allocation 	OUTCOME	
Level of Masking:	 Double-masked 	Primary:	 Transfusion of packed RBCs or maternal death
Stratification:	 Clinical site 	Secondary:	 Composite of treatments for blood loss
Sample Size:	❖ 11,000	,	 Estimated blood loss Transfusion of other blood products
Assumptions:	 Outcome event=transfusion of packed RBCs or maternal death Placebo group event rate = 2.5% TXA group event rate = 1.67% (33% reduction) Type I error = 5% (two sided) Power = 85% 		 Transfusion of other blood products Transfusion-related morbidities Thromboembolic events Change in hemoglobin from baseline
		TIMETABLE	
Interim Analysis:	 Lan-DeMets group sequential method 	Enrollment: Data Collection: Closeout/Analysis	 November 2017 to October 2020 November 2017 to December 2020 January 2021 to August 2021

References

- 1. Organization WH. The World Health Report, 2005: Make Every Mother and Child Count. Geneva: World Health Organization; 2005.

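### Do asymmetric interim boundaries of one-sided 0.025 and 0.05 contradict the stated two-sided 5% type I error?

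*Combined protocol and SAP*

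**What the plan says.** Section 5.2 (Sample Size and Power) calculates its table "using a two-tailed alpha of 0.05". Appendix A lists, among the design assumptions beside the event rates and the power, "Type I error = 5% (two sided".

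Section 5.4 (Interim Analysis) adopts Lan-DeMets spending and announces: "Asymmetric stopping boundaries will be used for the Lan-DeMets procedure". For the first boundary: "The upper boundary which describes the stopping rule for benefit will be based on 1-sided type I error of 0.025", with O'Brien-Fleming-type spending. For the other: "The lower boundary will be based on a less stringent stopping rule: 1-sided type I error of 0.05", with Pocock-type spending.

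The number and timing of looks are left open: "This method is flexible with regard to the timing of the interim analyses". Section 5.4 also says that a decision to stop would rest on clinical as well as statistical considerations. The plan gives no combined error for the two boundaries, and it does not say whether the lower one also applies at the final analysis. It does not use the word harm for the lower boundary; that reading follows because it is the side opposite to benefit.

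**The concern.** A two-sided 5% test is normally read as 2.5% in each direction. Section 5.4 describes both of its amounts as type I error, and they add to 7.5%, with the unfavourable side given twice its usual share. Section 5.5 (Analysis Plan) names no significance level for the primary comparison, so a reader must take it from one of the places that differ.

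If the total error were really above the stated level for the claim the trial is meant to support, the sample size, the power and the efficacy conclusion would all be in doubt. Short of that, a crossing of the lower boundary might be reported as significant at two-sided 5% when that side alone carries up to 5%.

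**Working it through.** **Inputs.** From Section 5.2 and Appendix A: placebo rate 2.5%, TXA rate 1.67%, two-sided alpha 0.05, power 85%, 11,000 women (5,500 per arm), Poisson approximation. From Section 5.4: upper spend 0.025 (O'Brien-Fleming type), lower spend 0.05 (Pocock type). Assumption: 2 to 5 equally spaced analyses including the final one, because the plan fixes no number.

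**1. The plan's own figure.** With z(0.975) + z(0.85) = 1.960 + 1.036 = 2.996, squared 8.978:

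N = 2 × 8.978 × (p1 + p2) / (p1 − p2)²

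- At 1.67%: 2 × 8.978 × 0.0417 / 0.0083² ≈ 10,869.
- At an exact one-third reduction: 10,774.
- At a 33% reduction (1.675%): 11,015.

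Power at 5,500 per arm and 1.67%: 0.0083 / √(0.0417 / 5,500) = 3.014; 3.014 − 1.960 = 1.054, giving 85.4%. The stated 11,000 and 85% are reproduced.

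**2. Which boundary the sample size matches.** The calculation uses the critical value 1.960, which is the two-sided 0.05 value and equally the one-sided 0.025 value. It therefore agrees with the benefit boundary. Under the boundaries themselves, with 2, 3 and 4 analyses, power for a one-third reduction is 85.5%, 85.2% and 85.0%. At 1.67% it is 85.2%, 84.9% and 84.7%.

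**3. The combined error.** The trial can first cross only one boundary, so the null probabilities add: 0.025 + 0.05 = 0.075. Numerical integration of the null path gives 0.025 upper, 0.050 lower and 0.075 in total for 2, 3, 4 and 5 analyses. This requires the lower spend to be completed at the final look.

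**4. If the lower boundary acts only at interim looks.** Pocock-type spending by information fraction t is 0.05 × ln(1 + (e − 1)t).

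| Analyses | t at last interim | Lower spent | Total with 0.025 upper |
|---|---|---|---|
| 2 | 0.50 | 0.0310 | 0.056 |
| 3 | 0.67 | 0.0382 | 0.063 |
| 4 | 0.75 | 0.0414 | 0.066 |
| 5 | 0.80 | 0.0432 | 0.068 |

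If the final lower critical value instead mirrors the upper one, the totals are 0.071, 0.075, 0.076 and 0.076.

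**5. The benefit side.** Its error is 0.025 in every variant above. It stays at 0.0250 even if a lower crossing is overruled and the trial continues, since a path that reaches the lower boundary almost never later crosses the upper one under the null.

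**6. What the lower boundary looks like in practice.** With full spending, the lower critical values are −1.868 and −1.886 for 2 analyses; −2.004, −1.996 and −1.982 for 3; and −2.102, −2.079, −2.055 and −2.036 for 4. From 3 analyses on, every value already lies beyond −1.96.

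**The case for a change.** The best argument for acting is that disclosing the asymmetry does not disclose its effect on the error rate stated elsewhere. The total exceeds 5% in every variant checked; only a lower spend of 0.025 brings it to 5.0%. Section 5.5 gives no level. In Section 5.4, the condition that opens formal testing of estimated blood loss mentions significance of the primary outcome without a direction, and only its second limb refers to benefit. A few sentences would settle all of this.

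Much of that is accurate, and the lack of an explicit link between the two statements stands. It does not carry a change. The hypothesis in Section 1.2 and the question in Section 3.1 are directional, so an analyst would open the secondary test on a favourable primary result at the 0.025 boundary. No sentence says that a lower crossing would be declared significant at two-sided 5%, and Section 5.4 treats stopping as a judgement for which the boundary is one input. The wording that would be added mostly repeats levels already printed in Section 5.4.

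The alternative, a lower spend of 0.025, is a trade-off and not a correction: it would restore the 5% total by making the trial slower to stop when the drug looks worse than placebo.

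**Conclusion.** The concern does not call for a change. The two one-sided levels do add to 7.5%, but the 5% figure is the sample-size convention, it is applied correctly, and it agrees with the benefit boundary. False benefit is held at 2.5%, and the 11,000 women and 85% power stand. The extra error, up to about 2.5 percentage points over a symmetric two-sided 5% design, falls on the unfavourable side by open design choice.

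The size depends on something the plan leaves open: 7.5% with full lower spending through the final analysis, 5.6% to 6.8% if the lower boundary acts only at interim looks, and 7.1% to 7.6% if the final lower value mirrors the upper. All assume 2 to 5 equally spaced analyses. Whichever applies, the efficacy conclusion is the same. A sentence describing 5% as the sizing and final-test convention would be harmless tidying, and nothing in the trial depends on it.

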Women will be contacted 1-2 weeks after delivery to inquire about signs and symptoms of deep vein thrombosis and pulmonary embolism (chest pain, shortness of breath, unilateral lower extremity swelling and tenderness) as well as incisional issues (wound drainage, separation, redness, fever, chills, and incisional pain). Education on thrombotic complications will also be reinforced.

Information on re-admissions, thromboembolic events, new onset seizure activity, and other peripartum complications will be collected during a patient telephone call or in person at a regular postpartum visit, 6 weeks after delivery by research nurses. If the patient's history is consistent with a thromboembolic event or taking anticoagulants, then the medical record will be obtained to confirm and assess the severity of the event.

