8.2 Recruitment and Data Collection Period

Approximately 160,000 women deliver in the MFMU Network annually. Using data from the APEX cohort, the rates of scheduled and unscheduled cesarean delivery were 12% and 20%, respectively. After excluding approximately 5% of women who would not meet eligibility criteria for the proposed trial, this leaves 18,240 eligible scheduled cesareans and 30,400 eligible unscheduled cesareans per year. For unscheduled cesarean deliveries it is assumed that only 20% are available for recruitment. This estimate allows for sufficient time for screening and consent (at least 2 hours) and that about 25% of unscheduled deliveries would be during normal office hours. Assuming only a third of eligible women consent to the

trial, approximately 2,000 women with unscheduled cesarean deliveries could be randomized annually. More scheduled cesarean deliveries are available for recruitment than unscheduled cesareans since the majority of scheduled deliveries are delivered during office hours, and there is more time for the screening and consent process. Since recruitment will be balanced between the two groups, approximately 4000 women can be randomized annually overall, which would mean that the trial could be completed in under 3 years.

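### The safety halt table is read against TXA women recruited rather than women observed, so its trigger rises too early at each row change, mainly at the first one or two, and a halt can be delayed.

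*Combined protocol and SAP*

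**What the plan says.** The halt rule in Section 5.4 (Interim Analysis) is monitored continuously by the coordinating center. It applies "If the number of such events that occur in the postpartum period meets the number in the table below". The table is headed "Number of Patients in TXA Group" and was built "assuming a 0.1% background rate of one of these events occurring post-cesarean delivery in the general population". The text says that "for each N (number of patients recruited), the smallest number of events was calculated", and gives the criterion as "the probability of the observed event rate occurring given the background rate is less than 5 percent". The rule does not state the length of the postpartum period or the window to which the 0.1% refers.

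The length has to be taken from elsewhere. Section 4.6.3 lists "Thromboembolic events (venous or arterial), ischemic stroke, or myocardial infarction within 6 weeks postpartum since the majority of events occur within 6 weeks" postpartum, and uses the same window for maternal death. Section 4.4 provides a contact at 1–2 weeks, and a last one at which thromboembolic events "will be collected during a patient telephone call or in person at a regular postpartum visit, 6 weeks after delivery by research nurses". Section 8.2 expects that "approximately 4000 women can be randomized annually overall".

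The plan allows for outcome delay in two other places. The feasibility look (Section 5.3) waits until the postpartum period is over for its 2,000 women. The efficacy interim (Section 5.4) uses a cohort defined by randomization date so that late reports do not distort it. The halt rule has no such provision.

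**The concern.** While recruitment runs, some of the N women are always inside their risk period. The table treats their unobserved time as event-free, so the denominator is too large for the events that could have been seen. The trigger therefore rises before the exposure it assumes has accrued, and the error always runs towards not halting. It is largest early on, when the women in the window are a large share of N and least is known about risk. At stake is how many further women are randomized before the DSMC is convened under this rule.

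**Working it through.** **Inputs.** Background rate p = 0.001; rows ending at 383, 905, 1537, 2239, 2992, 3782, 4601 and 5443 (Section 5.4). Allocation 1:1 (Section 3.6). 11,000 women, so about 5,500 on TXA (Section 3.3). 4,000 randomized per year, so 2,000 per year on TXA (Section 8.2). Assumed: a six-week window, steady accrual, and event timing as stated at each step.

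**1. Reproducing the table.** With X ~ Binomial(N, 0.001), the largest N at which trigger r still satisfies P(X = r) < 0.05 matches all eight cut-offs. For r = 2 the probability is 0.04997 at N = 383 and 0.05018 at 384. For r = 9 it is 0.04998 at 5,443 and 0.05001 at 5,444. The criterion is thus a point probability. The usual upper tail P(X ≥ r) < 0.05 would end the rows at 355, 818, 1367, 1971, 2614, 3286, 3982 and 4696. Under either criterion N is a set of women each carrying the full 0.1%.

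**2. Women in the window.** 2,000 × 42 / 365.25 = 230. If 11,000 women are spread over three years: (3,667 / 2) × 42 / 365.25 = 211.

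**3. Observed exposure at each row change.** Completed = N − 230. With even risk, each woman in the window counts one half on average, so full-follow-up equivalents = N − 115.

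| Trigger change | N recruited | Completed | Equivalents | P(X ≥ outgoing trigger) at N | Same, at equivalents |
|---|---|---|---|---|---|
| 2 → 3 | 384 | 154 (40%) | 269 | 5.7% | 3.0% |
| 3 → 4 | 906 | 676 (75%) | 791 | 6.4% | 4.6% |
| 4 → 5 | 1,538 | 1,308 (85%) | 1,423 | 7.0% | 5.6% |
| 9 → 10 | 5,444 | 5,214 (96%) | 5,329 | 10.1% | 9.2% |

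By the table's own criterion the outgoing trigger still applies at every change, because N − 115 lies below the row's cut-off each time. For example, P(X = 2) at 269 is (269 × 268 / 2) × 0.001² × 0.999²⁶⁷ = 2.8%.

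**4. How many recruitments are affected.**
- Against the table's criterion: 115 women after each of the first seven changes, plus those left after the eighth: 7 × 115 + (5,500 − 5,443) = 862, or 15.7% of 5,500.
- Against a true 5% upper tail: (355 + 115 − 383) + (818 + 115 − 905) = 87 + 28 = 115, or 2%. At the third change 1,367 + 115 = 1,482 is already below 1,537, so no shortfall remains. Against this standard the written trigger is too low, which makes a halt easier, for about 1,990 recruitments (36%).

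**5. Effect on halting.** Simulation of 5,500 TXA women at 2,000 per year, 4,000 runs per scenario (Monte Carlo standard error about 0.8 percentage points near 50%). The table is applied at each known event, once with N recruited and once with completers plus half of those in the window. Chance of a halt by 1,000 TXA women at a true rate of 0.3%:

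| Event timing | As written | Corrected count |
|---|---|---|
| Even over six weeks | 46% | 55% |
| All learned of at six weeks | 37% | 45% |
| Early (exponential, mean 10 days) | 51% | 59% |

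Allowing for a slower start-up as well, the ranges are 35–54% and 43–61%. With even risk and each woman weighted by the exact fraction of the window elapsed, the median halt moves from 1,136 to 931 TXA women. Over the whole recruitment period the halt probability is 98.5% against 98.7% at 0.3%, and 81% against 83% at 0.2%.

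**The case against.** Four points on the other side have force.

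- **Other safeguards.** A reader might infer that this table is the trial's only continuous protection. The documents do not support that. Section 4.5 requires thromboembolisms to be reported within 24 hours of notification and forwarded to the DSMC chair, and Section 5.4 adds a six-monthly safety review. The chair would know of two events at N = 384 without the table. What the table adds is an automatic halt between reviews.
- **The point-probability criterion is an offset.** It makes triggers easier to meet than a 5% tail would, and from the third change on this outweighs the lag (tails of 5.6% to 9.2% at the observed exposure). The inference that the rule is slower than a conventional 5% standard throughout is therefore wrong. The first two changes remain.
- **Eventual halting hardly changes.** A reader might infer that real harm would be missed, but step 5 shows a cost in time only. The early rows are also where 4,000 per year is least likely, since Section 8.1 requires each center to be certified before it recruits.
- **Window and timing are assumed.** Six weeks comes from other sections, and the documents give no distribution of event times. If events come early (mean 10 days), the true lag is about 2,000 / 365.25 × 10 = 55 women rather than 115, so part of the gain in that scenario is a lowered threshold rather than a corrected bias. When the corrected rule instead restricts both events and N to six-week completers, early timing shows almost no loss (82% against 82% halting at 0.2%), though that comparator discards early events.

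None of this removes the mismatch between recruited N and observed exposure. It limits its size.

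**Conclusion.** The point holds as a modest, inexpensive improvement to the safety rule. The table is indexed to recruitment while its risk assumption needs completed follow-up. At the planned pace the first change, from 2 to 3 events, comes with about 40% of the women through six weeks.

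Measured against the table's own criterion, the trigger is one event too high for about 860 of 5,500 TXA recruitments (16%). Multiplying 115 by all eight changes would give 920, but that counts women beyond the end of recruitment. Measured against a true 5% tail, the shortfall is confined to the first two changes.

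The practical effect is a later halt when there is a real excess: roughly 8 to 9 percentage points less chance of a halt by 1,000 TXA women at a true 0.3%. These figures rest on a six-week window, on enrolment near the projection, and on the three assumed timing patterns.

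**What to change.** Keep the table. In Section 5.4, state the length of the postpartum period that the rule counts, and that the 0.1% refers to the same period. Replace the number recruited, in the text and the column heading, with: TXA women who have completed that period plus half of those still within it. Count all known events against this number. The weighting is exact for even risk and somewhat cautious if events come early.

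The partial credit should be kept. Setting all known events against completers alone would make the rule too sensitive, with halts at the background rate of about 26%.

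The cost is a sentence or two and a count that the coordinating center can derive from delivery dates. At a true rate of 0.1%, pauses for DSMC review over the trial rise from about 20% to 23–24%. A pause leads to a review and does not by itself end the trial.
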